6.1.8. Complete Renal Response (LN Cohort Only)

To achieve CRR, participants in the LN cohort must meet all 3 of the following criteria:

- A decrease in mean UPCR to ≤ 0.5 g/g based on two 24-hour urine collections obtained within 2 weeks prior to the study visit (Week 26 or 50)
- eGFR > 60 mL/min/1.73 m² or no eGFR reduction ≥ 20% from the baseline value based on the mean of 2 values. The first eGFR value must be obtained within 2 weeks prior to the study visit (Week 26 or 50) and the second eGFR value will be obtained on the study visit (Week 26 or 50)
- No treatment failure

Only central laboratory results from both scheduled and unscheduled visits will be used to assess CRR.

In the presence of missing central laboratory values, the following rules will be applied:

- If only 1 nonmissing collection is available at the visit, then this value will be used for analysis.
- If both collections are missing at the visit, then CRR will be treated as missing.

Treatment failure is defined as the receipt of additional standard of care therapy at any time up during the study for protocol-defined renal flare, severe extrarenal SLE flare, or suboptimal response. Therefore, no treatment failure will be determined as the absence of additional standard of care therapy received at any time (Week 26 or 50) as recorded on the Additional Standard of Care Therapy eCRF.

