4.3.1.4. Complete Renal Response (LN Cohort Only)

Complete renal response (CRR) will be assessed at Weeks 26 and 50. To achieve CRR, participants in the LN cohort must meet all of the following criteria:

- A decrease in mean UPCR to ≤ 0.5 g/g based on two 24-hour urine collections obtained within 2 weeks prior to the study visit (Week 26 or 50)
- eGFR > 60 mL/min/1.73 m² or no eGFR reduction ≥ 20% from the baseline value based on the mean of 2 values. The first eGFR value must be obtained within 2 weeks prior to the study visit (Week 26 or 50) and the second eGFR value will be obtained on the study visit (Week 26 or 50)
- No treatment failure (as defined in Section 4.3.1.10)

The percentage of participants meeting the criteria for CRR as well as individual components of CRR will be summarized at Weeks 26 and 50 by treatment group by calculating the point estimate and 2-sided 95% CI, based on exact confidence limits using the Clopper-Pearson method.

Study participants with treatment discontinuation will be treated as failure to meet CRR criteria and considered nonresponders.

A bar chart will also be provided displaying the proportion of participants meeting the criteria for CRR as well as individual components of CRR at Weeks 26 and 50 by treatment group.

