4.3.1.5. Partial Renal Response (LN Cohort Only)

Partial renal response (PRR) will be assessed at Weeks 26 and 50. To achieve PRR, participants who did not achieve CRR in the LN cohort must meet all of the following criteria:

- Decrease in UPCR ≥ 50% compared to the baseline value based on mean of two 24-hour urine collections obtained within 2 weeks prior to the study visit (Week 26 or 50)
- eGFR > 60 mL/min/1.73 m² or no eGFR reduction ≥ 20% from the baseline value based on the mean of 2 values. The first eGFR value must be obtained within 2 weeks prior to the study visit (Week 26 or 50) and the second eGFR value will be obtained on the study visit (Week 26 or 50)
- No treatment failure (as defined in Section 4.3.1.10)

The percentage of participants meeting the criteria for PRR as well as individual components of PRR will be summarized at Weeks 26 and 50 by treatment group by calculating the point estimate and 2-sided 95% CI, based on exact confidence limits using the Clopper-Pearson method.

Study participants with treatment discontinuation will be treated as failure to meet PRR criteria and considered nonresponders.

A bar chart will also be provided displaying the proportion of participants meeting the criteria for PRR as well as individual components of PRR at Weeks 26 and 50 by treatment group.

4.3.1.6. Time to the First Occurrence of UPCR \leq 0.5 g/g (LN Cohort Only)

Time to the first occurrence of UPCR ≤ 0.5 g/g will be summarized by spot urine sample.

Participants will be censored at the earliest of their treatment discontinuation time, receipt of additional standard of care therapy (LN cohort only), study withdrawal or death, or at Week 50 when the event of UPCR ≤ 0.5 g/g has not yet occurred.

Kaplan-Meier will be used to estimate the survival curve. The corresponding Kaplan-Meier curve for each treatment group will be created by plotting the cumulative proportion surviving against the survival times.

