4.3.1.13. Partial Remission (IgAN Cohort Only)

For the IgAN cohort, partial remission will be defined as mean proteinuria < 1 g/24 hours based on 2 valid 24-hour urine collections obtained within 2 weeks prior to the study visit (Week 26 or 50).

The percentage of participants meeting the criteria for partial remission will be summarized at Weeks 26 and 50 by treatment group by calculating the point estimate and 2-sided 95% CI based on exact confidence limits using the Clopper-Pearson method.

Participants who discontinue treatment prior to the endpoint will be treated as failure to meet partial remission criteria and considered nonresponders.

A bar chart will also be provided displaying the proportion of participants meeting the criteria for partial remission at Weeks 26 and 50 by treatment group.

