6.1.10. Partial Remission (IgAN Cohort Only)

Partial remission will be defined as mean proteinuria < 1 g/24 hours based on 2 valid 24-hour urine collections obtained within 2 weeks prior to the study visit (Week 26 or 50).

Only central laboratory results from both scheduled and unscheduled visits will be used to assess partial remission.

In the presence of missing central laboratory values, the following rules will be applied:

- If only 1 nonmissing 24-hour urine collection is available at the visit, then this value will be used for analysis.
- If both collections are missing at the visit, then partial remission will be treated as missing.

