6.1.11. Partial Renal Response (LN Cohort Only)

To achieve PRR, participants who did not achieve CRR in the LN cohort must meet all of the following criteria:

- A decrease in UPCR ≥ 50% compared to the baseline value based on mean of two 24-hour urine collections obtained within 2 weeks prior to the study visit (Week 26 or 50)
- eGFR > 60 mL/min/1.73 m² or no eGFR reduction ≥ 20% from the baseline value based on the mean of 2 values. The first eGFR value must be obtained within 2 weeks prior to the study visit (Week 26 or 50) and the second eGFR value will be obtained on the study visit (Week 26 or 50)
- No treatment failure

Only central laboratory results from both scheduled and unscheduled visits will be used to assess PRR.

In the presence of missing central laboratory values, the following rules will be applied:

- If only 1 nonmissing collection is available at the visit, then this value will be used for analysis.
- If both collections are missing at the visit, then PRR will be treated as missing.

Treatment failure is defined as the receipt of additional standard of care therapy at any time up during the study for protocol-defined renal flare, severe extrarenal SLE flare, or suboptimal response. Therefore, no treatment failure will be determined as the absence of additional standard of care therapy received at any time (Week 26 or 50) as recorded on the Additional Standard-of-Care Therapy eCRF.

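### SAP 6.1 sets CRR, PRR and partial remission to missing when both 24-hour collections are absent, without excepting participants whose nonresponse is already determined

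*SAP*

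**What the plan says.** Two parts of the SAP determine these responder endpoints.

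**Derivation rules (Section 6.1).** Each rule follows a lead-in about missing central laboratory values.
- CRR, 6.1.8: "If both collections are missing at the visit, then CRR will be treated as missing".
- PRR, 6.1.11: "If both collections are missing at the visit, then PRR will be treated as missing".
- Partial remission, 6.1.10: "If both collections are missing at the visit, then partial remission will be treated as missing".

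**Analysis rules (Section 4.3.1).**
- CRR, 4.3.1.4: "Study participants with treatment discontinuation will be treated as failure to meet CRR criteria and considered nonresponders".
- PRR, 4.3.1.5: "Study participants with treatment discontinuation will be treated as failure to meet PRR criteria and considered nonresponders".
- Partial remission, 4.3.1.13: "Participants who discontinue treatment prior to the endpoint will be treated as failure to meet partial remission criteria and considered nonresponders".

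CRR and PRR each require every listed criterion to be met, and one criterion is the absence of Treatment Failure. SAP 6.1.8 states: "Treatment failure is defined as the receipt of additional standard of care therapy at any time up during the study", for renal flare, severe extrarenal flare or suboptimal response. That status is read from the Additional Standard of Care Therapy eCRF, not from urine.

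Three other sections bear on the point. SAP 4.4.8 makes participants with additional standard of care therapy or treatment discontinuation nonresponders for overall renal response (ORR), the composite of CRR and PRR. SAP 4.3.1.2 does the same for the >30% and >50% reductions in proteinuria. SAP 4.1.4 imputes nothing for post-baseline data missing for reasons other than intercurrent events, leaves intercurrent events to each analysis section, and assumes COVID-19 and dosing-pause missingness to be missing at random.

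**The concern.** A participant who has stopped treatment is more likely than others to have no Week 26 or Week 50 collection. Read literally, the SAP gives that participant two values, nonresponder under 4.3.1 and missing under 6.1, and neither section says which comes first. Section 6.1 is headed as the technical specification for derived variables, so a programmer could reasonably code the missing value.

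The LN Treatment Failure case is clearer. A participant who received additional standard of care therapy for a qualifying reason has already failed a necessary condition for CRR and PRR, so no urine result could change the outcome. Sections 6.1.8 and 6.1.11 nevertheless set it to missing. The nonresponder sentences in 4.3.1.4 and 4.3.1.5 name only treatment discontinuation, so nothing there rescues the outcome of a participant who is still taking study intervention.

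If missing responses leave the denominator, known failures are removed and response rates rise. They rise more in the arm that loses more failures.

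**Working it through.** The documents give no response rate and no expected number of participants with both collections missing, so there is no stated figure to reproduce. The check compares the rules and then illustrates their size.

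**Step 1: what each rule gives when both collections are missing**

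| Participant | Section 6.1 | Analysis section |
|---|---|---|
| LN, discontinued: CRR or PRR | missing | nonresponder (4.3.1.4, 4.3.1.5) |
| IgAN, discontinued: partial remission | missing | nonresponder (4.3.1.13) |
| LN Treatment Failure, still on treatment: CRR or PRR | missing | fails a required criterion; no explicit nonresponder sentence |
| The same LN participant: ORR | no rule | nonresponder (4.4.8) |
| Neither discontinued nor Treatment Failure | missing | no nonresponder rule |

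The first three rows are the problem and the last is not. Rows three and four show one person as a known ORR nonresponder while both components of ORR are missing.

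**Step 2: size, if missing means excluded**

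Inputs from SAP Section 5 are 30 participants per main LN arm, 24 per main IgAN arm, 10 in the LN 120 mg arm, and 10% dropout (0.10 × 30 = 3 per main LN arm). Responder counts x and the number affected m are assumptions. Here m counts participants with both collections missing who discontinued or, in LN, are Treatment Failures.

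- Nonresponder rule: x/N
- Missing excluded: x/(N − m)
- Inflation factor: N/(N − m)

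Main LN arm, x = 9:
- m = 0: 9/30 = 30.0% (Clopper-Pearson 95% CI 14.7 to 49.4)
- m = 1: 9/29 = 31.0%
- m = 3, every planned dropout without urine: 9/27 = 33.3% (16.5 to 54.0), factor 30/27 = 1.11

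Main IgAN arm, x = 10 (discontinuers only):
- m = 0: 10/24 = 41.7%
- m = 1: 10/23 = 43.5%
- m = 3: 10/21 = 47.6%

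LN 120 mg arm, x = 3:
- m = 0: 3/10 = 30.0%
- m = 1: 3/9 = 33.3%

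**Step 3: unequal loss between arms**

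Take 9 responders of 30 in both arms, with 3 affected in one and 6 in the other. Exclusion gives 9/27 = 33.3% against 9/24 = 37.5%, an apparent difference of 4.2 points. The nonresponder rule gives 30.0% in both.

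**Step 4: additivity with ORR**

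PRR is defined only for participants who did not achieve CRR, so the two are mutually exclusive and their rates should add to the ORR rate. If m participants are excluded from CRR and PRR but kept as nonresponders for ORR, the components sum to (x_CRR + x_PRR)/(N − m), while ORR is (x_CRR + x_PRR)/N. With any responders and m above 0, the reported rates would not add up.

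**The case against.** The strongest reply is that 4.1.4 already settles the discontinuation conflict. It leaves intercurrent events to each analysis section, Table 6 lists treatment discontinuation as an intercurrent event for these endpoints, and 4.3.1.4, 4.3.1.5 and 4.3.1.13 then assign nonresponse. On that reading, Section 6.1 derives the value and Section 4.3.1 overrides it. This is plausible and probably the intent for discontinuers. But 6.1 neither refers to 4.1.4 nor limits itself to other causes of missingness.

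For Treatment Failure, the reply is that the missing-data rule is introduced as being about laboratory values, and that failing one required criterion already means no CRR. The logic is right, but the rule sets CRR itself to missing, not just its laboratory component. Unlike 4.3.1.2 and 4.4.8, Sections 4.3.1.4 and 4.3.1.5 have no sentence on additional therapy to override it.

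The reply is also right that few participants may be affected. Protocol 7.1 asks discontinuers to continue visits through Week 50, Protocol 8.1.9 lets Treatment Failures stay in the study, and the combined Week 26/early discontinuation visit includes 24-hour urine.

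Three stronger readings are tempting, and the documents do not support them:
- A reader might infer that the SAP removes failures from the denominator. It does not say so. Section 4.3 bases these analyses on the FAS, and if FAS N is always the denominator the percentage does not change.
- A reader might extend the Treatment Failure argument to all three endpoints. Treatment Failure is defined for LN only, so partial remission in IgAN has only the discontinuation conflict.
- A reader might conclude that every missing result should count as nonresponse. That would turn COVID-19 and dosing-pause missingness into failures, against the missing-at-random assumption in 4.1.4.

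**Conclusion.** The point holds as a gap in precedence. Section 6.1 does not except participants whose nonresponse is already determined. For discontinuers in both cohorts the SAP can be reconciled through 4.1.4 but does not say so. For LN Treatment Failures still on treatment, following 6.1.8 and 6.1.11 as written gives the wrong value for CRR and PRR and disagrees with 4.4.8.

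Any inflation depends on an unstated denominator. If missing responses are excluded, the illustrative LN shift runs from 1.0 point (one participant affected) to 3.3 points (all 3 planned dropouts without urine, an upper case under the dropout allowance), with 9 assumed responders. Both are small beside a confidence interval about 35 points wide. Treatment Failures without urine would add to m, and the documents give no figure for them.

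Table 6 calls these analyses key secondary, but they are descriptive with no multiplicity adjustment, and the primary analysis is unaffected. This is a minor point, worth correcting because the correction is so cheap.

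**What to change.** - **6.1.8 and 6.1.11:** state that treatment discontinuation or Treatment Failure before the visit is applied first and gives nonresponder, whatever urine data exist.
- **6.1.10:** state the same for treatment discontinuation only.
- **All three sections:** limit the missing category to the remaining participants, for example those whose collections are absent because of COVID-19 or the dosing pause.
- **Denominator:** state whether participants left as missing stay in the FAS denominator for the percentage and its Clopper-Pearson interval.

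A matching sentence on additional standard of care therapy in 4.3.1.4 and 4.3.1.5 would bring them into line with 4.3.1.2 and 4.4.8. Do not adopt a blanket rule that every missing result is a nonresponse.

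The cost is a few sentences and a fixed order of steps in the derivation program, with no new data. Response rates may come out slightly less favourable.

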6.1.9. Concomitant Medications/Therapies

The analysis of concomitant medications and therapies is described in detail in Section 6.2.4.

Concomitant medications or therapies are defined as any nonstudy medications or therapies that were taken or given while the participant also received study intervention. A medication or therapy will be considered concomitant if the start date is on or after the date of the first dose of study intervention (Day 1), or if the start date is before the first dose of study intervention and the end (stop) date is after the first dose of study intervention. If the start date of a medication/therapy is partially or completely missing and the end (stop) date of the medication/therapy does not indicate that it ended prior to first dose of study intervention, then the determination of the concomitant status will be based on the following:

- If the start year is after the year of the first dose of study intervention, then the medication/therapy is concomitant; else,
- If the start year is the same as the year of the first dose of study intervention and
 - The start month is missing, then the medication/therapy is concomitant; else,
 - If the start month is present and is the same or after the month of the first dose of study intervention, then the medication/therapy is concomitant; else,
- If the start date is completely missing, then the medication/therapy is concomitant

All other medications/therapies are considered prior medications/therapies.

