4.1.4. Handling of Dropouts or Missing Data

No imputation will be performed for missing baseline values. For missing postbaseline data not due to IEs, no imputation will be performed.

To derive duration of disease, partial date of diagnosis will be imputed as follows:

- If day is missing, it will be imputed to the "01"
- If day and month are missing, they will be imputed to "January 01"

Partial concomitant medication start dates and AE start dates will follow the same imputation rule to derive study phase.

Missing outcome data due to the COVID-19 pandemic (eg, dropout due to COVID-19) is assumed missing-at-random (MAR).

Missing outcome data due to dosing pause is assumed MAR.

Missing data for quality-of-life (QoL) instruments will be handled as specified in the instructions for each instrument in Section 6.3.

The following may occur during the study:

- Receipt of additional standard-of-care therapy (LN cohort only)
- Treatment discontinuation (LN and IgAN cohorts)
- Dosing pause

The handling of IEs is detailed in each analysis section.

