4.6.4. Subgroup Analyses

Summaries of the primary efficacy endpoint will be presented by the following subgroups for both cohorts:

- Age at Screening (18 to 65 years, > 65 years)
- Sex (female, male)
- Baseline eGFR ($\leq 60, > 60-90, > 90 \text{ mL/min/}1.73 \text{ m}^2$)
- Baseline C3/C4 (at least 1 C3/C4 low, no low C3/C4) Assessment method (in-clinic or alternative method)
- Concomitant therapy with SGLT-2 inhibitors (Yes, No), optional for LN cohort

For the LN cohort, summaries of the primary efficacy endpoint will be presented by the following additional subgroups:

- Duration of disease (≤ 1 year, > 1 year)
- Race/ethnicity (African American, non-African American)
- Baseline proteinuria ($\leq 3.5 \text{ g/g}$, > 3.5 g/g)
- Corticosteroid induction timing (prior to Screening, during Screening Period)

- LN class based on central pathology (III or III/V, IV or IV/V)
- TMA on renal biopsy based on central pathology (yes, no)
- Disease status (naïve, relapse)
- Baseline renal biopsy activity index based on central pathology (≤ median, > median)
- Baseline renal biopsy chronicity index based on central pathology (≤ median,
 > median)

For the IgAN cohort, summaries of the primary efficacy endpoint will be presented by the following additional subgroups:

- Duration of disease (≤ 1 year, 1-5 years, > 5 years)
- Race (Asian or Other Pacific Islander, non-Asian or Other Pacific Islander)
- Baseline proteinuria (1-2 g/day, > 2 g/day)
- Baseline MEST-C score based on central pathology (M0, M1, E0, E1, S0, S1, T0, T1, T2, C0, C1, C2)
- Baseline C3 staining based on central pathology (presence, absence)
- Assessment method (in-clinic or alternative method)

For the IgAN cohort, summaries of the primary efficacy endpoint by subgroups of baseline MEST-C score and baseline C3 staining will be presented separately for participants with biopsies within 1 year of randomization and for participants with biopsies greater than 1 year before randomization if feasible based on sample size.

Given that the number of participants in some subgroups may be limited, subgroup categories may be combined as appropriate. Otherwise, the subgroup analysis may not be performed if deemed infeasible based on sample size.

Forest plots will be produced showing the results of the primary efficacy endpoint (percentage change in proteinuria from baseline to Week 26) with means and corresponding CIs for each subgroup described above.

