6.2.4. Prior and Concomitant Medications

Prior and concomitant medications and procedures will be summarized using the SS.

Prior medications and/or vaccines (including vitamins, herbal preparations, and those discussed in the eligibility criteria in Protocol Section 5) and procedures (eg, surgery, biopsy, physical therapy) are those received or underwent ≤ 30 days prior to Screening or during the Screening Period, as well as any meningococcal vaccine administered within the last 3 years.

Concomitant medications (including any medication, vitamin, herbal preparation, or supplement) and procedures defined in Protocol Section 6.5) are those received on or after the first study intervention date (Day 1), including those started before Day 1 and continued after Day 1.

Medications will be coded using the World Health Organization Drug Dictionary (WHO-DRUG) version in use by Alexion at the time of the analysis, while nonpharmacologic therapies and procedures (any therapeutic intervention, such as surgery/biopsy or physical therapy) will be coded using MedDRA version 26.1 or later.

Prior medication and concomitant medication, summaries will be presented by WHO-DRUG anatomical therapeutic chemical (ATC) Level 3 and by WHO-DRUG generic name using number and percentage of participants by treatment group. Procedures will be summarized similarly but presented by MedDRA Class and PT. In addition, protocol-required vaccinations will be summarized similarly.

By-participant listings of prior and concomitant medications, procedures, and protocol-required vaccinations will also be produced.

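### SAP 6.1.9 classes an ongoing medication as prior only when its partial start date falls before the month of first dose, against the SAP's own overlap definition

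*SAP*

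**What the plan says.** **Complete dates.** SAP 6.1.9 (Concomitant Medications/Therapies) defines concomitant use by overlap with study intervention. A drug begun earlier still counts "if the start date is before the first dose of study intervention and the end (stop) date is after the first dose". SAP 6.2.4, which governs the medication tables, has the same scope, "including those started before Day 1 and continued after Day 1", and Protocol 8.2.5 agrees with it.

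**Partial or missing start dates.** A record enters a separate rule in 6.1.9 when the stop "date of the medication/therapy does not indicate that it ended prior to first dose of study intervention". Ongoing drugs therefore enter. The branches are then:

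1. "If the start year is after the year of the first dose of study intervention, then the medication/therapy is concomitant".
2. Same year as first dose: concomitant if the month is missing, or is the first-dose month or later.
3. Start date completely missing: concomitant.
4. "All other medications/therapies are considered prior medications/therapies".

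**A second rule.** SAP 4.1.4 sets a missing day to the 1st, and a missing day and month to 1 January, and adds: "Partial concomitant medication start dates and AE start dates will follow the same imputation rule to derive study phase".

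**A third version.** Protocol 9.4.4 classes anything begun before first dose as prior, and reserves concomitant for drugs begun on or after it.

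**The concern.** In the partial-date rule the stop date only admits a record; no later branch uses it. The question then becomes when the drug began, although the definition asks whether its use overlapped with study intervention. The branches closely resemble the adverse-event rule in SAP 6.1.7, where onset is the right question. For medications it is not.

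The resulting order is hard to defend. A drug known to have begun before Day 1 and known to be ongoing is not concomitant, while one with no start date is.

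Long-term drugs are the ones exposed, and the design contains several. Protocol 5.1.3 asks for RAS inhibition at a stable dose for at least 3 months before Screening. Protocol 5.1.1 requires at least 3 months of stable dosing for participants on SGLT-2 inhibitors. Protocol 6.5.1 strongly recommends antimalarials such as hydroxychloroquine in the LN cohort. At stake are the accuracy of the concomitant medication tables and whether two programmers working from this SAP would produce the same ones.

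**Working it through.** The plan states no figure on this point, so there is none to reproduce. The check applies the rules literally.

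**Step 1. Run the rules on each date pattern.** Assumed first dose: 15 June 2023. The drug is ongoing, which is read as a stop date after first dose. The last column imputes the start date by 4.1.4 and then applies the complete-date rule of 6.1.9.

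| Recorded start | 6.1.9 partial-date rule | 4.1.4, then complete-date rule |
|---|---|---|
| 2019, month and day missing | prior | concomitant |
| March 2019, day missing | prior | concomitant |
| December 2022, day missing | prior | concomitant |
| February 2023, day missing | prior | concomitant |
| 2023, month and day missing | concomitant | concomitant |
| June 2023, day missing | concomitant | concomitant |
| August 2023, day missing | concomitant | concomitant |
| Completely missing | concomitant | no rule given |

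Three kinds of pattern go wrong: earlier year with month and day missing, earlier year with only the day missing, and an earlier month of the first-dose year with the day missing. With a complete start date, every one of these drugs is concomitant under 6.1.9 itself.

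**Step 2. How often a partial date on a long-term drug lands in those patterns.** This is an illustration. Assume first dose is uniform over the calendar year. Assume the drug began between 3 months (91 days) and L years before a 42-day screening, uniformly. The lag from start to first dose then runs from a = (91 + 42)/365.25 = 133/365.25 = 0.364 years to b = L + 42/365.25 = L + 0.115 years.

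- *Only the day missing.* A lag of at least 133 days always puts the start in an earlier month, so 100% are classed prior.
- *Day and month missing.* The record is classed prior when the start falls in an earlier calendar year. For a lag of d years this has probability min(d, 1). Averaging over the lag:

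 share = [(1 − a²)/2 + (b − 1)] / (b − a), with (1 − 0.364²)/2 = 0.434

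| L (years) | Calculation | Classed prior |
|---|---|---|
| 1 | (0.434 + 0.115)/0.751 | 73% |
| 2 | (0.434 + 1.115)/1.751 | 88% |
| 5 | (0.434 + 4.115)/4.751 | 96% |
| 10 | (0.434 + 9.115)/9.751 | 98% |

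These are shares of partial-date records. They are not shares of participants or of all records, because the documents do not say how many start dates will be partial.

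**Step 3. Where the flag is used.** SAP 6.2.4 tabulates prior and concomitant medications, and 6.1.9 refers to it, so those tables depend on the flag directly. SAP 4.6.4 lists the subgroup "Concomitant therapy with SGLT-2 inhibitors (Yes, No), optional for LN cohort", and 6.2.2.2 lists SGLT-2 use as a baseline characteristic; neither says how it is derived. The primary ANCOVA in SAP 4.2.2 has no term based on the flag.

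**The case against.** **Section 4.1.4 may already solve it.** If partial start dates are imputed first, the complete-date rule gives the right class for every dated record. That is true, as the last column of the first table shows. But 4.1.4 states its purpose as deriving study phase, 6.1.9 has its own explicit rule for the same dates, and nothing ranks the two. The conflict stands.

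**Protocol 9.4.4 supports prior.** It does, for any drug begun before first dose. It cannot rescue 6.1.9, which uses overlap for complete dates and calls a drug with no start date concomitant. SAP 4.8 records one departure from the protocol, the hematuria variable, and not this one. The objection adds a third text to reconcile.

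**The consequences are small.** This largely stands. The tables are descriptive, and SAP 6.2.4 also provides by-participant listings of prior and concomitant medications, so no record is lost.

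A reader might go further and infer that RAS inhibitors, SGLT-2 inhibitors and hydroxychloroquine disappear from the concomitant outputs. The documents do not support that. Only partial-date records are affected. SAP 6.2.5 separately tabulates allowed concomitant therapy, including RAS blockers in IgAN: before Screening, at baseline, and as changes during the study. SGLT-2 use has its own entries. Of the three, hydroxychloroquine alone has no separately specified output.

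A reader might also infer a count of participants per arm shown as untreated. That would need a partial-date rate that the documents do not give, and Protocol 5.1.3 admits RAS-intolerant participants. Nor does any text tie the Per-Protocol Set, or the check that allowed therapy was stable, to this flag.

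**Conclusion.** The rule is wrong as written, and the defect is minor. On a literal reading of 6.1.9, every ongoing medication whose partial start date shows an earlier year, or an earlier month of the first-dose year, is classed prior only. That contradicts 6.1.9's own definition, SAP 6.2.4 and Protocol 8.2.5, and it disagrees with what 4.1.4 would produce.

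The direct effect, if 6.1.9 is followed, is under-counting of those records in the concomitant medication tables. The number cannot be stated. Under the assumed start-date spreads, most partial dates on long-term drugs would be affected: all of those lacking only the day, and 73% to 98% of those lacking day and month. The SGLT-2 subgroup and baseline summary are at risk only if programmed from the same flag. The primary test is not affected.

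**What to change.** In SAP 6.1.9, replace the partial-date branches and the closing line with one rule. A medication with a partial or missing start date is concomitant unless its stop date, or the latest date compatible with a partial stop date, is before first dose. State that a drug begun before Day 1 and ongoing counts as both prior and concomitant.

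Then:

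- say that this rule takes precedence over 4.1.4 for prior/concomitant classification, leaving 4.1.4 for study phase;
- list the departure from Protocol 9.4.4 in SAP 4.8.

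With the rule in place, all eight patterns in the first table become concomitant, as the SAP's own definition requires. The cost is a few sentences in the SAP and a change to one derivation program. No new data are needed.
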